Abstinence at 4 weeks post TQD is defined as a self-report of no smoking of conventional cigarettes (not a puff) for the previous 2 weeks, validated by a CO reading of <8ppm. Participants who do not provide a CO reading at Week 4 will be considered to be smoking at 4 weeks. 24 and 52 week sustained abstinence will be calculated in accordance with the Russell Standard [6] as a self-report of smoking no more than 5 cigarettes since 2 weeks post TQD, validated by CO readings of <8ppm at the 52 week follow up. Participants lost to follow up or not providing biochemical validation will be included as non-abstainers.

Study methods

Overall study design and plan

Target for randomisation:	886
Date of first randomisation:	11.05.2015
Date of last randomisation:	01.02.2017
Trial design:	Individually randomised, parallel group
Who is blinded:	Participants and researchers are blinded up until the point of randomization.
Randomised Interventions:	Intervention (EC) vs. control (NRT)
Allocation ratio:	1:1

Study population

The study population consisted of people responding to advertising (typically posters, leaflets, digital media, local papers, on local transport, through GP practices, mail outs to previous attendees, and in local radio/newspaper interviews).

Participants were eligible to take part if they were age 18 years and older, a current smoker accessing a stop smoking service (SSS) and able to read/write/understand English.

Participants were excluded from participating if they were pregnant or breastfeeding, had a strong preference to use or not to use NRT or EC in their quit attempt, were enrolled in other interventional research, or currently using NRT or EC.

Method of treatment assignment and randomisation

Randomisation (1:1 in permuted blocks) was undertaken using a web-based application, set up by the Barts Clinical Trials Unit (Barts CTU), and was stratified by study site. Participants who were eligible and consent to take part were randomly allocated to the experimental or control interventions at the target quit day (TQD) session. The TQD was used as the point of randomisation to limit any differential drop-out. The staff randomising the patient accessed the web-based application when the participant was with them, entering their participant ID number, date of birth and initials into the program. There were no stratification factors within study sites. The allocation was immediately provided by the program.

Treatment masking (Blinding)

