| 1. CO validated sustained abstinence between 24 and 52 weeks post TQD | 
No more than 5 cigarettes smoked between weeks 24 and 52 accompanied by a CO reading of < 8ppm at week 52.
 
Where a participant reports being 'currently quit' at 52 weeks post TQD, but has not been contactable to provide any other information, they will not be counted as a 24-52 week sustained abstainer, since they will not have been contactable to arrange a CO validation.
 |
| 2. CO validated sustained abstinence at 4-weeks post TQD | 
Not a single puff of a cigarette in the last 2 weeks at 4 week follow up accompanied by a CO reading of < 8ppm at 4 weeks post TQD.
 
Where a participant misses Q+3 but reports not a single puff since their last visit at 4 weeks post TQD, accompanied by a CO reading of < 8ppm at 4 weeks post TQD, they will be counted as a CO validated abstainer at 4 weeks post TQD.
 
Where a participant reports being 'currently quit' at 4 weeks post TQD, but has not been contactable to provide any other information, they will not be counted as a 4 week abstainer since they will not have been contactable to arrange a CO validation.
 |
| 3. Sustained abstinence at 24 weeks post TQD | 
No more than 5 cigarettes smoked since 2 weeks post TQD to 24 weeks post TQD.
 |

Where a participant misses any (or all) of the previous sessions/follow ups, but self-reports smoking no more than 5 cigarettes since their last visit at 24 weeks post TQD, they will be counted as a 24 week sustained abstainer

Where a participant reports smoking 1-5 cigarettes at more than one session/follow up but reports smoking no more than 5 cigarettes in total since their last visit at 24 week follow up, they will be assumed to have smoked less than 5 cigarettes in total since 2 weeks post TQD.

Where a participant reports being 'currently quit' at 24 weeks post TQD, but has not been contactable to provide any other information, they **will** be counted as having smoked no more than 5 cigarettes since their last visit, and included as a 24 week sustained abstainer.

- | | |
|---|--|
| 4. 7-day point prevalence at 4-weeks post TQD | Not a single puff in the last 7-days |
| 5. 7-day point prevalence at 24-weeks post TQD | Not a single puff in the last 7-days |
| 6. 7-day point prevalence at 52-weeks post TQD | Not a single puff in the last 7-days |

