Q2 (CO reading) on Q+4 post Quit CRF (only for those who attended Q+4 in person and self-reported abstinence). NB. As per definition in primary outcome section, those who do not provide a CO reading at 4 weeks post TQD but self-report abstinence at this time point will be assumed to be abstinent at 52 weeks follow up providing they report no more than 5 cigarettes smoked since 2 weeks post TQD at 52 weeks accompanied by a CO reading of < 8ppm at week 52. Those who self-report abstinence at 4 weeks post TQD but fail CO validation at 4 weeks post TQD (> 8ppm) will **not** be counted as abstinent at 52 week follow up.

At Q+52:

Q3. Since two weeks after your quit date, have you smoked regular cigarettes at all? (circle ONE)

1. Not a single puff
2. Just a few puffs
3. ≤ 5 cigs in total
4. > 5 cigs in total

NB. as per definition in primary outcome section, where a participant reports smoking 1-5 cigarettes at more than one session/follow up but reports smoking no more than 5 cigarettes in total since 2 weeks post TQD at 52 week follow up, they will be assumed to have smoked no more than 5 cigarettes in total since 2 weeks post TQD and will meet the primary outcome definition providing their self-report is validated by a CO reading of <8ppm at the 52 week follow up.

Where a participant reports being 'currently quit' at 52 week follow up, but has not been contactable to provide any other information, they will be not counted as a 52 weeks sustained abstainer since they will not have been contactable to arrange a CO validation.

Where a participant reports being 'currently quit' at 4 and/or 24 weeks post TQD and has not been contactable to provide further information at these time points, but then reports smoking no more than 5 cigarettes in total since 2 weeks post TQD at 52 week follow up, they will be assumed to have smoked no more than 5 cigarettes in total since 2 weeks post TQD and will meet the primary outcome definition providing their self-report is validated by a CO reading of <8ppm at the 52 week follow up.

Q+52 Validation Visit CRF

2. Record carbon monoxide in expired breath (ppm)

Secondary Outcomes

1. CO validated sustained abstinence between 24 and 52 weeks post TQD

Definition: No more than 5 cigarettes smoked between weeks 24 and 52 accompanied by a CO reading of < 8ppm at week 52.

Data source: Q+52 CRF

Have you smoked regular cigarettes at all in the last 6 months? (circle ONE)

1. Not a single puff
2. Just a few puffs

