3. ≤ 5 cigs in total
4. > 5 cigs in total
5. Currently quit – no other info

NB. Where a participant reports being 'currently quit' at 52 week follow up, but has not been contactable to provide any other information, they will be not counted as a 24-52 week sustained abstainer since they will not have been contactable to arrange a CO validation.

Q+52 Validation Visit CRF

3. Record carbon monoxide in expired breath (ppm)

2. CO validated sustained abstinence at 4 weeks post TQD

Definition: Not a single puff of a cigarette in the last 2 weeks at 4 week follow up accompanied by a CO reading of < 8ppm at 4 week follow up.

Data source: Q+3 and Q+4 CRF

Q3. Have you smoked regular cigarettes at all since your last visit/contact? (circle ONE)

1. Not a single puff
2. Just a few puffs
3. ≤ 5 cigs in total
4. > 5 cigs in total
5. Currently quit – no other info (shown at Q+4, 24 and 52 only)

NB. As per the definition in the secondary outcomes section, where a participant misses Q+3 but reports not a single puff since their last visit at 4 weeks post TQD, accompanied by a CO reading of < 8ppm at 4 weeks, they will be counted as a CO validated abstainer at 4 weeks post TQD.

Where a participant reports being ‘currently quit’ at 4 weeks post TQD, but has not been contactable to provide any other information, they will not be counted as a 4 week abstainer since they will not have been contactable to arrange a CO validation.

Q2. Record carbon monoxide in expired breath (ppm) on Q+4 post quit CRF only

3. Sustained abstinence at 24 weeks post TQD

Definition: No more than 5 cigarettes smoked since 2 weeks post TQD at 24 weeks

Data source: Q+3, Q+4 and Q+24 CRF

Have you smoked regular cigarettes at all since your last visit/contact? (circle ONE)

1. Not a single puff
2. Just a few puffs
3. ≤ 5 cigs in total
4. > 5 cigs in total
5. Currently quit – no other info (shown at Q+4, 24 and 52 only)

NB. As per definition in secondary outcome section, where data is missing for 3 and/or 4 weeks post TQD participants will be assumed to be abstinent at 24 weeks post TQD providing they report no more than 5 cigarettes smoked since their last visit at 24 weeks.

Where a participant reports smoking 1-5 cigarettes at 3 and 4 weeks post TQD but reports smoking no more than 5 cigarettes in total since their last visit at 24 weeks, they will be assumed to have smoked less than 5 cigarettes in total since 2 weeks post TQD at 24 weeks.

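### The 24-week sustained-abstinence rule assumes a total since week 2 that no week-24 question measures, so some participants over the 5-cigarette limit can count as abstinent

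*SAP*

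**What the plan says.** The SAP's Outcome measures section ties both time points to one standard: "24 and 52 week sustained abstinence will be calculated in accordance with the Russell Standard", with a limit of 5 cigarettes since week 2. Under Definitions of smoking cessation and reduction outcomes, secondary outcome 3 repeats the limit: "No more than 5 cigarettes smoked since 2 weeks post TQD to 24 weeks post TQD". Its definition there requires no CO reading at week 24.

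Appendix 3 takes this outcome from the Q+3, Q+4 and Q+24 forms. The item is "Have you smoked regular cigarettes at all since your last visit/contact? (circle ONE", answered in bands: not a puff, a few puffs, up to 5 cigarettes, more than 5, or (not at Q+3) currently quit with no other information.

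The rule for repeat reporters says that where someone with 1-5 cigarettes at more than one contact reports no more than 5 "in total since their last visit at 24 week follow up, they will be assumed to have smoked less than 5 cigarettes in total" since week 2. Appendix 3 restates it for a narrower case: "Where a participant reports smoking 1-5 cigarettes at 3 and 4 weeks post TQD but reports smoking no more than 5 cigarettes in total" since the last visit at week 24.

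The 52-week outcome has a similar rule, but the Q+52 item reads "Since two weeks after your quit date, have you smoked regular cigarettes at all".

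**The concern.** The limit is cumulative over 22 weeks, whereas the week-24 answer covers only the time since the last contact. For someone seen at week 4, the Q+24 answer carries no information about weeks 2 to 4, and that is where the other reports of 1-5 cigarettes lie. The rule nevertheless treats a low week-24 answer as settling the whole total. It also settles it at fewer than 5, which is not the outcome's own limit of 5 or fewer.

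At stake is whether the 24-week row of Table 5, which carries a risk ratio and p-value, measures what its label says. Some repeated lapsers may be counted as sustained abstainers, with no CO reading at week 24 to catch them. The sensitivity analysis listed specifically for the secondary outcomes concerns the replacement EC device and does not address this.

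**Working it through.** The plan gives no figure for this rule, so there is none to reproduce. The check is which totals the rule admits.

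**Inputs**
- Limit: total from week 2 to week 24 of 5 or fewer (secondary outcome 3).
- Contacts at weeks 2, 3, 4 and 24 (Timing of data collection).
- Each item looks back to the last contact (Appendix 3, outcome 3).
- 443 per arm (Sample size determination).

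**Step 1: windows.** For a participant seen at Q+2, Q+3, Q+4 and Q+24, the answers cover about weeks 2-3, 3-4 and 4-24. These do not overlap, so total = a + b + c, where a, b and c are the cigarettes smoked in each window.

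**Step 2: range of totals under the rule**
- Appendix 3 case (a and b each 1-5, c 0-5): minimum 1 + 1 + 0 = 2; maximum 5 + 5 + 5 = 15. Of the 5 × 5 × 6 = 150 whole-number combinations, 20 are 5 or fewer (10 of them fewer than 5) and 130 exceed 5.
- 1-5 at all three contacts: totals 3 to 15. Of 125 combinations, 10 are 5 or fewer (4 of them fewer than 5) and 115 exceed 5.
- 1-5 at two contacts only, none at the third: totals 2 to 10. Of 25 combinations, 15 exceed 5.

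These count possible combinations. They do not estimate how many participants are affected, because the combinations are not equally likely.

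**Step 3: examples.** 5 + 5 + 0 = 10 and 3 + 3 + 0 = 6 both break the limit and both count as abstinent. 1 + 1 + 0 = 2 keeps the limit and is classified correctly.

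**Step 4: missed contacts.** If Q+3 is missed, the Q+4 answer covers weeks 2-4 and the maximum falls to 5 + 5 = 10. If both Q+3 and Q+4 are missed, the Q+24 answer reaches back to week 2 or earlier and no excess can arise. If Q+2 is missed, the Q+3 answer reaches back before week 2 and may include smoking that does not count against the outcome.

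**Step 5: contrast with week 52.** The Q+52 item covers weeks 2 to 52. Since the total for weeks 2-24 cannot exceed the total for weeks 2-52, a Q+52 report of 5 or fewer also shows that the 24-week limit was met. The converse fails: more than 5 by week 52 does not show more than 5 by week 24.

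**Step 6: size.** One percentage point of an arm is 0.01 × 443 = 4.4 participants. If the number wrongly counted as abstinent differs between arms by d, the risk difference shifts by d/443. For assumed values of d = 1, 5 and 10, that is 0.2, 1.1 and 2.3 percentage points.

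**The case against.** The strongest reply is that the forms record bands. Ticking up to 5 cigarettes twice or three times is compatible with a true total of 5 or fewer, so the rule resolves an ambiguity, and it says openly that it is an assumption. It applies identically to both arms and was set in advance. This stands in part: the limit is breached only for an unknown share of those covered. But the rule resolves every ambiguous case in one direction, and the SAP offers no alternative analysis.

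A second reply concerns the obvious remedy, counting every repeat reporter as a smoker. Under the 52-week rules, a participant with several reports of 1-5 cigarettes meets the primary outcome if the Q+52 answer is 5 or fewer and CO is below 8 ppm. The blunt remedy would make that person abstinent from week 2 to 52 but not from week 2 to 24. It would also misclassify someone who smoked 1 + 1. This objection stands and shapes the fix.

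A reader might infer that the rule biases the 24-week risk ratio towards one arm. The SAP does not support that: it gives no count of repeat reporters and no reason to expect them to be commoner in either arm. Identical application does not guarantee balance, but imbalance is only a possibility.

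**Conclusion.** The rule is wrong as written. It assigns a total below 5 to participants whose answers fit totals from 2 to 15, up to three times the limit, and no week-24 item measures that total. The maximum of 15 assumes that Q+2, Q+3, Q+4 and Q+24 were all attended and that the top of the band was reached at each of the last three. The number affected is unknown, as is the direction of any effect on the treatment comparison.

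The reach is narrow: one secondary outcome. A reader might suspect the parallel 52-week rule too, but there the participant reports directly on the whole period since week 2 and CO is measured at week 52, so this defect does not touch the primary outcome. The gap between fewer than 5 and no more than 5 is a wording slip, to be corrected at the same time.

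**What to change.** In secondary outcome 3 and in Appendix 3, outcome 3:

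1. Delete the assumption of fewer than 5 cigarettes and use no more than 5 throughout.
2. For participants who tick up to 5 cigarettes at two or more of Q+3, Q+4 and Q+24, use the Q+52 since-week-2 answer where available. A report of 5 or fewer means the 24-week limit was met. This keeps their 24-week status consistent with the primary outcome.
3. For the rest, including those with no Q+52 answer or one above 5, state that the total is not measured. Report the 24-week result with all of them non-abstinent and with all of them abstinent, and name in advance which is the main result.
4. State how the currently-quit answer is handled for these participants, and how a Q+3 answer is treated when Q+2 was missed.

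Report the number of unresolved cases by arm. The two analyses bound each arm's rate for this group but not strictly the risk ratio, whose extremes need opposite assignments in the two arms. Step 2 resolves cases only towards abstinence and depends on week-52 follow-up, another reason to show the counts.

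The cost is one derived variable and one sensitivity analysis on data already collected, and a slightly lower 24-week rate if unresolved cases are counted as smokers in the main result.

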- The number of participants included in the analysis, by treatment group. NB. for the primary outcome data this will be all randomised participants – see missing data section below);
- A summary measure of the outcome, by treatment group (e.g. mean (SD) for continuous outcomes, number (%) for binary outcomes);
- A treatment effect (risk ratio of abstinence for EC relative to NRT), with a 95% confidence interval;
- A two-sided p-value.

Missing data for outcomes

To deal with incomplete data (i.e. when patients have missing data at one of the follow-up time points) we will:

- Attempt to follow up all randomised patients even if they discontinue participation.
- Include participants lost to follow-up (missing cases) or not providing biochemical validation as non-abstainers.
- Carry out a sensitivity analysis using different assumptions about missing cases (e.g. using the Hedeker method [15] and last known quit status), as well as analyses excluding cases with missing outcomes. NB. Where a participant misses 52 week follow up, but it is already known from their 3, 4 and/or 24 week follow up that they have smoked more than 5 cigarettes since 2 weeks post TQD, they will be counted as smokers for the primary outcome in sensitivity analyses.

Withdrawn participants

Withdrawn participants (i.e. no further follow up permitted) will be included in the analysis as per intention to treat (counted as smokers for the time points after withdrawal, as per Russell Standard).

Participants who died will be excluded from the sample as per the Russell Standard.

Participants who have moved to an untraceable address (documented by returned letters) and whose telephone numbers and email address are no longer in use will be excluded from the sample from the point that notification was received that they were no longer living at the address and their telephone numbers/email address are no longer in use, as per the Russell Standard. They will be included in the sample analysis up until this point.

Analysis of primary outcome

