- Where a participant misses any (or all) of the previous sessions/follow ups, but self-reports smoking no more than 5 cigarettes since 2 weeks post TQD at 52 week follow up, they will be classed as meeting the primary outcome definition providing their self-report is validated by a CO reading of <8ppm at the 52 week follow up.
- Where a participant reports smoking 1-5 cigarettes at more than one session/follow up but reports smoking no more than 5 cigarettes in total since 2 weeks post TQD at 52 week follow up, they will be assumed to have smoked no more than 5 cigarettes in total since 2 weeks post TQD and will meet the primary outcome definition providing their self-report is validated by a CO reading of <8ppm at the 52 week follow-up.
- Where a participant self-reports abstinence at 4 weeks post TQD, but does not give a CO reading at this time point, and at 52 week follow up self-reports smoking no more than 5 cigarettes since 2 weeks post TQD, they will be classed as meeting the primary outcome definition providing their self-report is validated by a CO reading of <8ppm at the 52 week follow-up.

- Where a participant self-reports abstinence at 4 weeks post TQD but fails CO validation at this time point (i.e. they have a CO reading of greater than 8 at 4 weeks post TQD), they will not be included as a CO validated sustained abstainer at 52 week follow up.
- Where a participant reports being 'currently quit' at 52 week follow up, but has not been contactable to provide any other information, they will **not** be counted as a 52 week sustained abstainer, since they will not have been contactable to arrange a CO validation.
- Where a participant reports being 'currently quit' at 4 and/or 24 weeks post TQD and has not been contactable to provide further information at these time points, but then reports smoking no more than 5 cigarettes in total since 2 weeks post TQD at 52 week follow up, they will be assumed to have smoked no more than 5 cigarettes in total since 2 weeks post TQD and will meet the primary outcome definition providing their self-report is validated by a CO reading of <8ppm at the 52 week follow-up.

Secondary outcomes:

- | | |
|---|---|

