Where a participant reports being 'currently quit' at 24 weeks post TQD, but has not been contactable to provide any other information, they will be counted as having smoked no more than 5 cigarettes since their last visit, and included as a 24 week sustained abstainer.

4. 7-day point prevalence
at 4-weeks post TQD

Definition: Not a single puff in the last 7-days

Data source: Q+4 CRF

If you have smoked since your last visit/contact, did you smoke at all in the last 7 days?

1. Yes
2. No

5. 7-day point prevalence
at 24-weeks post TQD

Definition: Not a single puff in the last 7-days

Data source: Q+24 CRF

If you have smoked since your last visit/contact, did you smoke at all in the last 7 days?

1. Yes
2. No

6. 7-day point prevalence
at 52-weeks post TQD

Definition: Not a single puff in the last 7-days

Data source: Q+52 CRF

Have you smoked at all in the last 7 days?

1. Yes
2. No

7. Smoking reduction in participants who did not achieve abstinence at 52 weeks

Definition: Daily cigarette consumption of at least 50% of baseline consumption accompanied by a CO reading of 50% of baseline

Data source: Q+52 Post Quit CRF

3b. How many cigarettes per day are you smoking now?

3c. Percentage reduction in number of cigarettes smoked from start of study

Q+52 Validation Visit CRF

3. Record carbon monoxide in expired breath (ppm)

NB. Where participants have CO<10 at baseline and report 50% or more cigarette per day reduction at 52 weeks post TQD, sensitivity analyses will be carried out including and excluding them.

A sub-analysis of self-reported daily cigarette consumption at 52 week follow up reduced by at least 50% of baseline consumption without accompanied CO readings will also be conducted.

Data source: Q+52 Post Quit CRF

3b. How many cigarettes per day are you smoking now?

3c. Percentage reduction in number of cigarettes smoked from start of study

8. Changes in urges to smoke and other tobacco withdrawal symptoms at 1 and 4 weeks.

Definition: Differences in the ratings of urge frequency at 1 and 4 weeks post quit on following scale: not at all, a little of the time, some of the time, a lot of time, almost all of the time, all of the time.

Differences in the ratings of urge strength at 1 and 4 weeks post quit on following scale: no urges, slight, moderate, strong, very strong, extremely strong.

Data source: Q+1 and Q+4 Post Quit CRF

Q6. How much of the time have you felt the urge to smoke over the past week?

1. Not at all

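### 24-week sustained abstinence has two incompatible definitions, and a bare 'currently quit' counts as meeting it without any information on the cigarette limit

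*SAP*

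**What the plan says.** The SAP describes the 24-week outcome in several places.

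- **Secondary outcome measures, closing paragraph.** "24 and 52 week sustained abstinence will be calculated in accordance with the Russell Standard", and the same sentence ends "validated by CO readings of <8ppm at the 52 week follow up". The next sentence adds: "Participants lost to follow up or not providing biochemical validation will be included as non-abstainers".
- **Secondary outcome measures, numbered list.** CO validation is attached to week 4 only.
- **Definitions of smoking cessation and reduction outcomes, secondary outcome 3.** "No more than 5 cigarettes smoked since 2 weeks post TQD to 24 weeks post TQD". No CO reading is mentioned.
- **Table 5.** The rows for sustained abstinence at 4 weeks, 24 to 52 weeks and 52 weeks are labelled as CO validated. The 24-week row is not.
- **Appendix 3, item 3.** The data sources are the Q+3, Q+4 and Q+24 forms, again without CO.

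Secondary outcome 3 also says how to score a participant who reports being currently quit at 24 weeks and cannot be reached for anything more: they are "counted as having smoked no more than 5 cigarettes since their last visit, and included as a 24 week sustained abstainer". Appendix 3 repeats this. At week 4, for 24 to 52 weeks, and for the primary outcome, the same answer is not counted, "since they will not have been contactable to arrange a CO validation".

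The general rule under Missing data for outcomes is: "Include participants lost to follow-up (missing cases) or not providing biochemical validation as non-abstainers".

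**The concern.** There are two separate faults in one outcome.

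First, an analyst who follows the closing paragraph of the outcome section needs a clean CO reading at week 52 before calling anyone abstinent at week 24. A participant who was abstinent at 24 weeks and relapsed at month 9 would then be a failure at 24 weeks, and the outcome would move towards the primary one. An analyst who follows the definitions section would use self-report. Both would be following the SAP, and their results would differ.

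Second, 'currently quit' describes a moment. The outcome concerns the whole period from week 2 to week 24. The form gives this answer its own category, separate from those that report how much was smoked, so it holds no information on the criterion. Scoring it as success can create false abstainers.

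Table 5 reports the outcome with a risk ratio and p-value. It is unvalidated, and participants know their allocation (Treatment masking). The analysis listed specifically for secondary outcomes concerns the 42 participants given a different device. The sensitivity analyses for missing cases would not clearly reach the bare answer, because the rule has already classified it.

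**Working it through.** **1. Does the bare-answer rule establish the definition?** The criterion is a count: at most 5 cigarettes from week 2 to week 24. The bare answer supplies no count. The rule imputes one, but only back to the last visit. If that visit was Q+4, the imputed span is 24 − 4 = 20 weeks, and weeks 2 to 4 must come from the Q+3 and Q+4 forms. Those forms are listed as data sources and offer an answer of more than 5 cigarettes. However, the rule goes straight on to include the person as a sustained abstainer, and no sentence says that such an earlier report prevails.

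Elsewhere the SAP treats the answer as uninformative. For smoking reduction (secondary outcome 7), participants who say only that they are currently quit are grouped with those who have missing data. For the primary outcome, a bare answer at 24 weeks is accepted only once a cigarette report and a CO reading at week 52 are supplied.

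**2. Anchor.** The SAP states no rate, power or count for the 24-week outcome, so there is no figure to reproduce. Its power for the primary outcome serves as a check on the inputs: 443 per arm, 10% v 17%, two-sided 5%, pooled proportion 0.135.

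z = [0.07 − 1.96 × √(2 × 0.135 × 0.865 / 443)] / √[(0.10 × 0.90 + 0.17 × 0.83) / 443] = (0.0700 − 0.0450) / 0.0228 = 1.09, so power is 86.3%. The SAP states 86%.

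**3. How far apart are the two definitions?** Assumption: the SAP's 25% relapse between 6 and 12 months (Sample size determination) applies equally to both arms.

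| Reading | NRT | EC | RR | Power |
|---|---|---|---|---|
| Self-report at 24 weeks | 0.10 / 0.75 = 13.3%, 59 of 443 | 0.17 / 0.75 = 22.7%, 100 of 443 | 1.70 | 95% |
| CO at week 52 required | 10%, 44 of 443 | 17%, 75 of 443 | 1.70 | 86% |

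About 59 − 44 = 15 NRT and 100 − 75 = 25 EC participants change class. The ratio is unchanged only because equal relapse was assumed. Under the second reading the 24-week outcome has become the primary outcome.

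**4. What could the bare answer do?** The SAP gives no frequency. Assume that a share q of an arm gives this answer and that a fraction f of those had not sustained abstinence. Then

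RR = (0.2267 + q_EC × f) / (0.1333 + q_NRT × f).

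| q NRT | q EC | f | RR |
|---|---|---|---|
| 2% | 2% | 0.25 | 1.67 |
| 5% | 5% | 1.00 | 1.51 |
| 10% | 10% | 1.00 | 1.40 |
| 2% | 10% | 0.50 | 0.2767 / 0.1433 = 1.93 |
| 10% | 2% | 0.50 | 0.2367 / 0.1833 = 1.29 |

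With equal use, false abstainers per arm run from 443 × 0.02 × 0.25 = 2 to 443 × 0.10 × 1 = 44, and the ratio falls towards 1. With unequal use it moves either way. All values of q and f are assumptions, so the table shows only that the direction is not fixed.

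**The case against.** The best defence is that the bare-answer rule is deliberate. It is prespecified, the same for both arms, and stated twice. The SAP also gives its reason for rejecting the same answer at weeks 4 and 52: no CO reading could be arranged. No CO reading is planned at 24 weeks, so that reason does not apply there. A reader might infer that the SAP treats one answer inconsistently and without explanation; the text does not support that. What remains is narrower: the absence of CO explains why self-report is accepted, not why a missing self-report of consumption is.

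The 52-week CO sentence is probably loose drafting that merged two time points. The outcome list, detailed definition, Table 5 and Appendix 3 agree on self-report, and most analysts would follow them. It is therefore too strong to say that 24-week abstainers who relapse will in practice be scored as failures. Nor can both errors apply in full at once, since they belong to alternative readings. The contradiction still stands in the text.

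A reader might also infer bias towards EC. The SAP does not support this either. Support and follow-up contacts are identical by design (Summary), nothing suggests that the answer is commoner in one arm, and equal use pulls the risk ratio towards 1.

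Finally, scoring a known current quitter as a smoker also misclassifies those who truly sustained abstinence. The SAP cannot show which error is larger.

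**Conclusion.** The point holds as an inconsistency of definition with limited reach. The SAP contains two incompatible definitions of 24-week sustained abstinence, and a rule that awards the outcome on an answer that cannot establish it, with no stated precedence for earlier reports of more than 5 cigarettes.

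Some participants will be misclassified on this secondary outcome. The difference of about 15 NRT and 25 EC participants between the definitions depends on the SAP's planning rates and on equal relapse in both arms. The effect of the bare answer cannot be estimated from the SAP in size or direction. Risk ratios such as 1.51 or 1.93 illustrate assumed shares and should not be quoted as expected bias.

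The primary outcome is not affected, because it requires a cigarette report and a CO reading at week 52 whatever was said at 24 weeks.

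**What to change.** 1. In the closing paragraph of Secondary outcome measures, confine the 52-week CO requirement to the 52-week outcome, and state that the 24-week outcome is self-report.
2. In secondary outcome 3 and Appendix 3 item 3, state that a report at Q+3 or Q+4 of more than 5 cigarettes smoked after week 2 disqualifies a participant, whatever is answered at 24 weeks.
3. Score a bare 'currently quit' at 24 weeks as non-abstinent, in line with the rule for missing cases, and keep the present rule as a sensitivity analysis. At minimum, do the reverse. Which coding leads matters less than reporting both.
4. Report the number of such answers per arm.

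The cost is SAP wording and recoding; no new data are needed. The 24-week rate will be somewhat lower, and some participants who truly sustained abstinence will be counted as non-abstinent.
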